Official title of the study: Life-Skills Training Program: Its effect on Self-efficacy among Patients with Substance Use Disorders

NCT number: Pending

Date of the document: 1/4/2023

Introduction

Substance use disorders is episodic, with periods of abstinence, reduction of use, and relapse as the prevailing pattern, often with the course of events being influenced by external factors such as the availability of drugs and societal pressures (Sapkota, et al., 2019)

Self-Efficacy (SE) plays an essential role in the maintenance of abstinence from drugs and alcohol which is a belief regarding one's ability to successfully resist performing a behavior, and outcome expectancies, meaning the anticipated consequences of performing a behavior (Alanazi, et al., 2022). Also, Abstinence self-efficacy (ASE) as the belief individuals have in their ability to abstain from engaging in an undesired action. ASE includes an individual's level of confidence with their ability to abstain from substances for an extended period of time (Niles, et al., 2022).

Overall, Self-efficacy addresses the individual's perception of control of life events and is predictive of a person's goals and performance and affected with negative things such as shame (Bahramabadian, Mojtabaie, & Sabet, 2021).

Life skills are defined as a group of psychosocial competencies and interpersonal skills that help people make informed decisions, solve problems, think critically and creatively, communicate effectively, build healthy

relationships, empathize with others, and cope with and manage their lives in a healthy and productive manner (UNODC, 2023).

Life skills may be directed toward personal actions or actions toward others, as well as toward actions to change the surrounding environment to make it conducive to health (WHO, 2023). Bearing the WHO definition in mind, the Basic Life Skills curriculum offers youth the emotional, social, and intellectual tools needed to achieve success in life – on personal level, interpersonal level, also, within their community and workplaces (UNICEF. 2023)

Drug users often have problems with social and interpersonal relationships. The lack of adequate social relationships for patients' will should various negative personal and social consequences for patients' health, their families, friends, and society. Life skills training could effectively improve their social communication with parents, family, and friends. Life skills training should be part of addiction prevention training programs (Ebrahim, Radwan, & El Amrosy, 2022).

Life-skills training program designed to prevent substance use relapse which typically combine training about self-management skills (e.g., coping with stress), social skills (e.g., assertiveness), and skills to enhance resistance to substance use (e.g., opposing peer pressure to use substances) (Paz Castro, et al., 2022).

Participation in life skills workshops provides an opportunity for drug addicts to meet and communicate with others who have the same problem. The participants can share their remedies and approaches to deal with drug abuse, avoid recurrence, and handle cravings. They could provide multiparty support to improve the chance of keeping away from the drug. Moreover, intra-network social supports are against the sense of seclusion, isolation and foster interpersonal relationships (Jahanbin, et al., 2017)

Nurses are well placed to serve a key role in teams seeking to help individuals to avoid relapses. They often had critical knowledge about the community resources and trends. Also, their ability to provide a wide range of interventions ranging from supportive therapy to medical interventions often proves to be an asset to patients (Guenzel & McChargue, 2022)

Significant of the study

Substance use disorders are highly prevalent among youth and adult populations. It is estimated that 10% of adolescents and between 20% and 30% of adults (Centers for Disease Control CDC, 2021). The prevalence of substance use disorders is 5.9% in Egypt, the population between 15-25 is the most exposed to substance abuse and between 25-35 years is the most requested for treatment (Addiction Treatment and Abuse Fund, 2022). Relapse rates after treatment have been shown in other surveys to be as high as 40–75% in the 3 weeks to 6 months following treatment (Moradinazar, et al., 2020).

The recovery (management and rehabilitation) processes from substance use disorders are not inclusive enough and confine members to physical attendance for the purpose of detoxification, neglecting the important factors such as life skills, social, cultural, economic, environmental, and family factors. Since after detoxification of the substances users return to their family and society, there can't be expect a perfect quit without considering these factors carefully (Jepkorir, 2023).

Life skill educational program to enhance self-efficacy as a preventive approach in which it focuses on the development of personal and social skills. Previous studies revealed that there were few studies about the effects of life skills training on relapse prevention among patients with substances use disorders

(Volkow, 2020). Therefore, the present study is an attempt to introduce a safe and reasonable training program that help patients with substance use disorders to enhance abstinence self-efficacy.

Aim of the study

The study aims: to evaluate the effect of life-skills training program on self-efficacy among patients with substance use disorders.

The aim of this study will be achieved through the following objectives:

- 1- Assessing self-efficacy among patients with “substance use disorders”.
- 2- Assessing risk for relapse among patients with “substance use disorders”.
- 3- Developing life skills training program for self-efficacy among patients with substance-use disorders based on identified their needs.
- 4- Implementing the developed life skills training program of relapse prevention among patients with substance-use disorders.
- 5- Evaluating the effect of implementing life skills training program on self-efficacy among patients with “substance-use disorders”.

Research Hypothesis

Life skills training program will have a positive effect on self-efficacy among patients with substance-use disorders.

Subjects & Methods

Study design

A quasi-experimental research design on one group (pre-post) test will be used to conduct the current study.

Study setting

The study will be conducted at Alabbasya Mental Health Hospital in Cairo. It is the oldest and biggest hospital for psychiatric illnesses in Egypt, affiliated to General Secretariat of Mental Health and Addiction Treatment of the Ministry of Health. It was established in 1883 A.D over an area of 68 acres. Its capacity is 1950 beds. The hospital structure is divided into such as, sections: Twenty-one old free sections, four illegal sections (forensic), two new buildings one of them for males that included addiction treatment and rehabilitation department in new building (2nd -3rd -4th) floor included detox ward about 30 bed, rehabilitation ward 60 bed, and dual ward, and another one for females. also, clinics such as, outpatient clinic - addiction clinic - children clinic - adolescent clinic - daycare

clinic - aging clinic - dental clinic - electroencephalogram clinic and electro compulsive therapy clinic.

Subjects

A purposive sample will be obtained from patients with “substances use disorders” who meet inclusion criteria during their existence in the previously mentioned setting.

Inclusion criteria:

- Age: from 20 years to 50 years.
- Had history of one episode of relapse
- Free from any physical disease such as diabetes, hypertension, viral hepatitis etc.)
- Free from other Psychiatric disorders.

Sample size

Based on power analysis; Type I error (α) =0.05 with confidence level (1- α) =0.95 and Type II error (β) = 85%, by power test (1- β) =0.15, sample size was

calculated according to the following equation that has been adopted from (Gupta, et al, 2016)

$$N= 2(Z_{\alpha} + Z_{[1-\beta]})^2 \times SD^2/d^2$$

Where: n is the sample size, Z_{α} and $Z_{(1-\beta)}$ are constant values for convention values of α and β values where $Z_{\alpha} = 1.96$ when $\alpha = 0.05$ and $Z_{(1-\beta)} = 1.036$ when $\beta = 0.20$, SD is the standard deviation obtained from previous study Moshki, et al., (2014) and d is the effect size.

$$N= 2(1.96 + 1.03)^2 \times 7.7^2/5^2 = 42.4$$

Therefore, the minimal sample size was found to be =50 participants

Tools of data collection

Tool I: Interview Questionnaire

It will be designed by the researcher and reviewed by supervisors. It will be written in the Arabic language for gathering data in relation to the following parts:

Patients' characteristics. such as age, marital status, residence, qualifications, starting and years of substance use.... etc.

Clinical data (addiction History). about substances as types of substance, onset, duration, route, etc.

Tool II: Alcohol Abstinence Self-Efficacy Scale (AASE)

It was adapted by the researcher from DiClemente et al., (1994) to assess personal confidence against taken substance. It consists of 40 items for assessing self-efficacy. It includes 4 domain parts unranked: negative effect (1-5-9-13-17-21-25-29-33-37), social/positive situations (2-6-10-14-18-22-26-30-34-38), physical and other concern (3-7-11-15-19-23-27-31-35-39), and craving and urges(4-8-12-16-20-24-28-32-36-38). Every domain includes 10 items.

Scoring system. Each statement was rated on 5 points as a Likert Skill Scale ranged by statistical from (1) No Confidence, (2) Low Confidence, (3) Middle Confidence, (4) High Confidence, and (5) Excellent Confidence. The total score ranged from 40:200 ranged as, Low self-efficacy $40 < 120$, Middle self-efficacy $121 < 160$, and High self-efficacy $161 < 200$.

Validity:

The one tool will be formulated and submitted to (5) experts in psychiatric and mental health nursing or other specialty who will review the content of the tools for their comprehensiveness, accuracy, clarity, and relevance.

Reliability:

Cronbach's Alpha will be used to determine the internal reliability of the tool.

Preparatory Phase

This phase will be included reviewing of literature related to substance use disorder, relapse prevention, this served study tools for data collection. During this phase, the researcher also will be visited the selected place to be acquainted with the staff and the study settings.

Ethical considerations:

Research approval obtained from the faculty of Nursing- Ain Shams University Ethical Committee before starting the study. The researcher explained the aim and objectives of the study to patients with substance use disorder included in the study before starting. Written approval obtained from patients with substance use disorders before inclusion in the study. They guarantee that all the gathered data will be used confidentially and will be used for research purposes only. The researcher maintain anonymity and confidentiality of subjects' data included in the study. Patients with substance use disorder will be informed that they allow for withdrawal from study at any time.

Administrative design

Approval will be obtained through an issued letter from the dean of faculty of nursing to directors of the previously mentioned setting. The researcher will be met by the director to explain the purpose and methods of data collection and obtain participants consent of share in the study after explain anything such as, related to study and rights of withdrawal, free from harm. Data collected from the studied sample will be revised, coded, and entered using a personal computer (PC).

Computerized data entry and statistical analysis will be conducted using the statistical package for social sciences (SPSS).

Pilot study

The pilot study will be done on 10% (5 Patients) of the sample to examine the clarity of tools and to estimate time needed to fill in the study tools. Based on the results, modifications will be done (if necessary). Subjects included in the pilot study will be excluded from the study if major modifications are required.

Field work

- The researcher will explain the aim of the study and the components of the tools to the studied patients.
- The researcher will distribute a questionnaire to the studied patients to assess their self-efficacy.
- The researcher will distribute a questionnaire to the patients studied to assess the risk of relapse.
- The researcher trained patients in improving their life-skills.

Life-skills Training Program

Life-Skills Training program will be developed by the researcher and reviewed by supervisors for Enhance self-efficacy among patients with substance use disorders. After reviewing the past and current related literature through

teaching the patients how to identify, plan and participate in relapse prevention. The program will cover an overview of substance use disorders, relapse prevention, self-efficacy, and many of life skills such as problems solving, assertiveness, negotiation, refusal, time management, meditation, emotional regulations, and non-violence communication skills.

Results

The results of the study will be presented in tables and figures that are easy to understand and will be analyzed for inferring information and the proper comments will be stated.

Discussion

The results will be discussed in the light of available national and international studies.

Conclusion

It will be derived from the finding of the study based on the research hypothesis.

Recommendations

It will be derived from the discussion based on the findings of the study.

Summary

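### The aim and hypothesis claim an effect of the program, but an uncontrolled one-group pre-post design can show only that self-efficacy changed

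*Protocol*

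**What the plan says.** The Study design section of the protocol reads: "A quasi-experimental research design on one group (pre-post) test will be used to conduct the current study". No comparison group or repeated baseline is described.

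The Aim is "to evaluate the effect of life-skills training program on self-efficacy among patients with substance use disorders", and objective 5 repeats it. The Research Hypothesis is "Life skills training program will have a positive effect on self-efficacy among patients with substance-use disorders". The Conclusion section says only: "It will be derived from the finding of the study based on the research hypothesis". No sentence restricts the conclusion to a before-after difference.

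The Study setting section describes an addiction treatment and rehabilitation department that "included detox ward about 30 bed, rehabilitation ward 60 bed". Patients are recruited while they are in this hospital. The section also lists outpatient, addiction and daycare clinics, so inpatient status is not stated outright.

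Under Field work the researcher explains the aim to patients. Next, "The researcher will distribute a questionnaire to the studied patients to assess their self-efficacy", and later in the same list, "The researcher trained patients in improving their life-skills". The Life-skills Training Program section says that the researcher also develops the program. The outcome (Tool II) is the patient's own rating of confidence: 40 items scored 1 to 5, total 40 to 200. The protocol does not say who gives or scores the post-test.

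**The concern.** The pre-post difference is a sum: program effect, other hospital care, passage of time (including days abstinent), re-testing, and any wish to please the person who explains the aim and does the training. With one group and one pre-test, no analysis can split that sum. This is therefore not a detail that could be left to a statistical analysis plan: the protocol itself fixes the design, the hypothesis and the basis of the conclusion.

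The protocol also gives reason to expect change without the program. Its Introduction describes the disorder as episodic and shaped by external factors, and recruitment takes place where other addiction care is offered.

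At stake is the study's only hypothesis. A significant rise would be reported as an effect of the program even if the program did nothing.

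**Working it through.** **1. The plan's own figure.** From the Sample size section: Z values 1.96 and 1.03, SD 7.7, difference d = 5.

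N = 2 × (1.96 + 1.03)² × 7.7² / 5² = 2 × 8.9401 × 59.29 / 25 = 42.4.

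This reproduces the stated 42.4, which the protocol then sets to a minimum of 50. The point made here does not depend on this figure. It supplies only N = 50, SD = 7.7 and d = 5 for the illustration below.

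**2. What the change estimates.** Post minus pre = program effect + background change, where background change covers usual care, time, re-testing and demand effects. If the program effect is zero, the test of no change is a test of the background change.

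**3. How often background change alone would be significant.** Inputs:
- N = 50 and two-sided α = 0.05 (Sample size; 1.96 implies two-sided).
- A paired t test: assumed, since the protocol names no test.
- SD of change 7.7 or 10.9: assumed. If 7.7 is the SD at each visit and r is the pre-post correlation, SD of change = 7.7 × √(2(1 − r)). This gives 7.7 at r = 0.5 and 7.7 × √2 = 10.9 at r = 0.
- Background rise of 1, 2, 3 or 5 points: assumed. Five points equals the protocol's d.

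Noncentrality = rise / (SD of change / √50), 49 degrees of freedom, critical value 2.01. Example: 3 / (7.7 / 7.07) = 2.75, which gives 77.1%.

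| Background rise (points) | SD of change 7.7 | SD of change 10.9 |
|---|---|---|
| 0 | 5.0% | 5.0% |
| 1 | 14.7% | 9.7% |
| 2 | 43.7% | 24.6% |
| 3 | 77.1% | 47.9% |
| 5 | 99.4% | 88.9% |

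The score runs from 40 to 200, a range of 160 points, so a rise of 3 points is 3/160 = 1.9% of the range.

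**4. Would a second pre-program questionnaire rescue the causal claim?** The corrected contrast is (post − pre2) − (pre2 − pre1) = post − 2·pre2 + pre1, with equal intervals. With equal variances σ² and equal correlations r, its variance is 6σ²(1 − r), against 2σ²(1 − r) for a simple change. Its SD is therefore √3 times the SD of change: 13.3 or 18.9. At d = 5 and N = 50 the noncentrality is 2.65 or 1.87, and power is 74% or 45%. The simple change has 99% or 89%.

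**The case against.** **The design is openly declared.** The protocol calls itself quasi-experimental, with one group. That is true, and choosing such a design is not in itself an error. But the label softens neither the hypothesis nor the conclusion, and no caveat is planned.

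**The Conclusion sentence is generic.** It sets no decision rule. This stands, and the weight rests on the wording of the aim and hypothesis. The Conclusion sentence shows only that nothing later in the document weakens them.

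**The percentages do not size the problem in this trial.** This also stands. The rise, the SD of change and the test are all assumed. The SD of 7.7 is taken from a cited study whose title concerns preventive behaviors among university students, and the protocol gives no SD for the 40–200 scale.

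Three stronger readings are tempting, and the document does not support them:
- A reader might infer that the type I error is inflated. It is not: a test of no change rejects 5% of the time when nothing changes. The table shows power to detect a real change that the program did not cause.
- A reader might infer that all patients are inpatients. The Study setting section also lists clinics. Other hospital care may contribute in either case.
- A reader might infer that the trainer collects and scores the post-test. Field work says only that the researcher distributes the questionnaire, in a list that places this before the training. Demand effects are plausible because the researcher also explains the aim, develops the program and trains, but the post-test arrangement is unstated.

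**Conclusion.** The point holds as a mismatch between claim and design. The protocol states a causal aim and hypothesis that one group with a single pre-test cannot support, and it contains no limiting statement. This follows from the text alone and needs no assumption about the size of any background change.

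The illustration shows that the mismatch could matter. With no program effect, a background rise equal to the protocol's own d of 5 points would be significant in about 89–99% of studies of 50 patients, and a rise of 2 points in about 25–44%. These figures are conditional on the assumed SD of change and on a paired t test. They are not estimates for this trial.

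**What to change.** Reword the Aim, objective 5, the Research Hypothesis and the Conclusion so that each refers to change, for example: *self-efficacy changes from before to after the life-skills program*. Add one sentence saying that the design has no control and cannot attribute the change to the program. This needs no extra patients, staff or visits. The price is a weaker claim.

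A second questionnaire before the program starts could be offered as an optional supportive analysis, not as the main result. It assumes linear background drift and needs a waiting period, and the protocol gives neither length of stay nor program duration by which to judge whether that is feasible. With equal intervals, its power at d = 5 with 50 patients is only about 45–74%.

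Sealing the pre-test forms from the trainer until the last post-test would reduce demand effects, but it is not recommended as things stand. Objective 3 builds the program on patients' identified needs, which may require sight of the pre-test answers. The two would have to be reconciled first.

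### The protocol fixes a purposive sample with no rule for which eligible patients are approached, so selection may affect the baseline levels and the uncontrolled pre-post change, by an unknown amount and in an unknown direction

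*Protocol*

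**What the plan says.** - **Sampling (Protocol, Subjects).** "A purposive sample will be obtained from patients with" substance use disorders "who meet inclusion criteria during their existence in the previously mentioned setting". Four inclusion criteria follow: age 20 to 50, a past relapse, no physical disease and no other psychiatric disorder. There is no consecutive, random or all-eligible rule, no start date and no screening or refusal log.
- **Setting (Protocol, Study setting).** One hospital, whose addiction services include a detox ward of about 30 beds, a 60-bed rehabilitation ward, a dual ward and an addiction clinic. The target is 50 participants (Sample size).
- **Design (Protocol, Study design).** "A quasi-experimental research design on one group (pre-post) test will be used to conduct the current study".
- **Objectives (Protocol, Aim of the study).** Objective 1 is "Assessing self-efficacy among patients with" substance use disorders. Objective 2 is "Assessing risk for relapse among patients with" the same disorders. Objective 5 is "Evaluating the effect of implementing life skills training program on self-efficacy among patients with" them.
- **Who does what (Protocol, Field work and Life-skills Training Program).** The researcher develops the program and hands out the questionnaires, and "The researcher trained patients in improving their life-skills". The protocol does not say who decides which patients are invited.

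**The concern.** The four criteria define who may enter. They do not decide between a detox and a rehabilitation patient, or between two eligible patients on one ward. Under a purposive method that choice is left open, and it could matter in two ways.

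1. **Level.** If the patients approached differ from the other eligible patients, the baseline self-efficacy and relapse-risk figures describe those approached and not the hospital's eligible patients. A control group would not repair this.
2. **Change.** If patients are approached because they seem low at the time, their scores would tend to rise at the second measurement without any program. If they are approached because they seem cooperative, they may respond better than others would. With no comparison group, nothing subtracts either effect from the pre-post difference.

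A larger sample removes neither effect.

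**Working it through.** **Step 1. The plan's own figure.** The Sample size section computes N = 2(1.96 + 1.03)² × 7.7² / 5². This is 2 × 8.9401 × 59.29 / 25 = 42.40, which agrees with the stated 42.4. It has no bearing on selection. It is used here only because it is the protocol's sole source for an SD (7.7) and a difference (5).

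**Step 2. What the documents allow to be computed.** Size and direction of any selection effect depend on how the patients approached differ from the other eligible patients. The protocol gives nothing on this: no criterion uses the self-efficacy score, and neither need nor expected response is a criterion. No estimate of bias can be derived.

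**Step 3. Illustration under assumptions.** Assumptions, none of them from the protocol:
- scores are normal;
- selection takes the lowest fraction f on the baseline score itself;
- the test-retest correlation r is 0.5 to 0.9;
- the SD of 7.7 applies to the trial's scale.

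Formulas, with c the normal quantile at f and φ the normal density:
- baseline shift = −7.7 × φ(c) / f
- spurious gain = (1 − r) × 7.7 × φ(c) / f

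| Lowest fraction selected | Baseline shift | Gain, r = 0.9 | Gain, r = 0.7 | Gain, r = 0.5 |
|---|---|---|---|---|
| 90% | −1.50 | 0.15 | 0.45 | 0.75 |
| 75% | −3.26 | 0.33 | 0.98 | 1.63 |
| 50% | −6.14 | 0.61 | 1.84 | 3.07 |

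Check of one cell: for f = 0.5, c = 0 and φ(0) = 0.399, so the shift is −7.7 × 0.399 / 0.5 = −6.14. With r = 0.5 the gain is 0.5 × 6.14 = 3.07.

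Against the planning difference of 5, the gain runs from 0.15 / 5 = 3% to 3.07 / 5 = 61%.

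**Step 4. The other cases.** If selection is unrelated to current state or expected response, shift and spurious gain are both zero. If higher scorers are chosen, both signs reverse and regression to the mean reduces the observed gain. Selection for expected response is not covered by these formulas.

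**The case against.** **The text can mean criterion-based sampling.** The sample is tied to patients who meet the inclusion criteria while in the setting, and a reader could take this to mean everyone who qualifies. This stands as far as it goes. A reader might infer that the researcher hand-picks patients, and the protocol does not support that: handing out questionnaires and training patients says nothing about who selects them. But the protocol does not say that all eligible patients are approached either.

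**Bias is not shown.** A reader might infer that the level and the gain are in fact biased. The documents support only a risk of unknown size and direction.

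**Any percentage is fragile.** Assuming a group that sits 0.5 to 1 SD low, with r of 0.7 to 0.5, gives 0.5 × 7.7 × 0.3 = 1.16 to 1 × 7.7 × 0.5 = 3.85 points, or 23% to 77% of 5. It is tempting to report this as the magnitude. It would require selecting about the lowest 70% or the lowest 38% on the score itself, which nothing in the protocol suggests. Selection on a rough impression would shift the score less. The SD of 7.7 comes from a cited study of university students and is not shown to be on the trial's 40 to 200 scale. The introduction's description of the disorder as episodic concerns drug use, not fluctuation of self-efficacy scores. All of this stands, so neither this range nor the table in the working is an estimate for this trial.

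**Objectives 1 and 2 may be needs assessment only.** The program is to be based on identified needs, and no prevalence is claimed. This is a fair reading and softens the point. Both objectives are nevertheless worded for patients with substance use disorders in general, and a reader cannot judge how far they apply without knowing who was approached.

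**Consecutive enrolment does not cure the change.** This is correct. Patients invited soon after admission may be at a low point, so regression to the mean and natural recovery would remain. For objective 5 the missing control group is the larger weakness.

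**Conclusion.** The point holds as a risk created by the stated sampling method. The protocol fixes a purposive sample and no rule limits the choice among eligible patients. The baseline levels for objectives 1 and 2 may therefore not represent the hospital's eligible patients. Because the only group is uncontrolled, selection may also affect the pre-post change used for objective 5.

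Size and direction cannot be determined from the protocol. The illustrative spurious gain of 0.15 to 3.07 points shows only that the effect could range from negligible to material against a planning difference of 5, if low scorers were favored and if the assumed correlations and the borrowed SD applied.

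This is a cheap improvement worth making. It settles who enters the sample, and leaves open whether the program caused any change.

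**What to change.** In the Subjects section, replace the purposive sample with consecutive enrolment: from a stated start date, every patient in the stated setting who meets the inclusion criteria is invited, in a stated order, until 50 have consented. Three additions go with it:

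- Keep and report a log of the numbers screened, eligible, invited, refused and enrolled.
- Keep the setting as the protocol defines it. If recruitment is meant to cover only certain wards, or to leave out the addiction clinic, say so. Say also whether dual-ward patients can meet the criterion that excludes other psychiatric disorders.
- Limit conclusions to the sampled group, and state that without a control group the pre-post change cannot be attributed to the program.

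The cost is a few sentences and a simple log, with no extra patients and no change of design. The one downside is that the researcher gives up discretion over whom to invite.

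### The sample-size section misstates the type II error and power: only beta = 0.15 with power 0.85 reproduces its own calculation

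*Protocol*

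**What the plan says.** All the figures are in the Sample size section of the protocol.

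- Type I error: "Type I error (α) =0.05 with confidence level (1- α) =0.95", with "Z_{\alpha} = 1.96$ when $\alpha = 0.05" in the definitions under the equation.
- Type II error and power, opening sentence: "Type II error (β) = 85%, by power test (1- β) =0.15".
- Type II error, definitions under the equation: "Z_{(1-\beta)} = 1.036$ when $\beta = 0.20".
- Equation: "N= 2(Z_{\alpha} + Z_{[1-\beta]})^2 \times SD^2/d^2".
- Worked line: "N= 2(1.96 + 1.03)^2 \times 7.7^2/5^2 = 42.4".
- Conclusion: "Therefore, the minimal sample size was found to be =50 participants".

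The Study design section describes a single group measured before and after the programme.

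**The concern.** Two different values of beta are stated in the same section, 85% and 0.20, and neither fits the Z value that the calculation uses. The opening sentence has beta and power the wrong way round. The definitions then label 1.036 with a beta that belongs to a different quantile. The stated power is therefore 15% in one place and 80% in another, while the Z implies 85%.

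This paragraph is the protocol's only justification for its sample size, and power is a central input to it. Anyone who copies the stated beta or power into a registry entry, an ethics file or a report will copy a figure that the calculation did not use.

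**Working it through.** **Inputs, all from the Sample size section.** Z for alpha = 1.96; Z for power = 1.03 in the worked line and 1.036 in the definitions; SD = 7.7; d = 5. So SD²/d² = 59.29/25 = 2.3716.

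**Reproducing the printed figure.** N = 2 × (1.96 + 1.03)² × 2.3716 = 2 × 8.9401 × 2.3716 = 42.405. This agrees with the printed 42.4.

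**What power does the Z imply?** With Phi the standard normal distribution function:

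- Phi(1.036) = 0.850 and Phi(1.03) = 0.848, so power is about 85% and beta about 0.15.
- Beta = 0.20 (power 0.80) needs Z = 0.842.
- Power 0.15 needs Z = -1.036.

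**N under each reading**, from N = 2(1.96 + Z)² × 2.3716:

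| Reading | Power | Z | N | Rounded up |
|---|---|---|---|---|
| Opening sentence, taken literally | 0.15 | -1.036 | 4.05 | 5 |
| Beta = 0.20 in the definitions | 0.80 | 0.842 | 37.2 | 38 |
| The Z value itself | 0.85 | 1.036 | 42.6 | 43 |

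Only the last row agrees with the printed result. The gap between 42.6 and 42.4 comes from shortening 1.036 to 1.03.

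**Does a one-sided test reconcile them?** No. With a one-sided alpha of 0.05, the same three powers give N = 1.8, 29.3 and 34.1, and none is 42.4. The value 1.96 fits a two-sided 0.05, although the section does not say so in words.

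**What does the planned 50 give under the same equation?** The sum of the two Z values is sqrt(50/(2 × 2.3716)) = sqrt(10.541) = 3.247. Subtracting 1.96 leaves 1.287, and Phi(1.287) is about 0.90. So by the protocol's own equation, 50 is above the N required under all three readings.

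**The case against.** The best defence is that this is a labelling slip and that the intended value is easy to recover. Swapping the labels in the opening sentence gives power 85% and beta 0.15. The Z of 1.036 gives the same, and the 1.03 in the worked line gives 84.8%. Only beta = 0.20 is out of line. The arithmetic reproduces, and no reading of beta makes 50 too few by the protocol's equation. All of that stands, and it limits the consequence. It does not make the stated figures right: the protocol prints two values of beta, and neither is the one it used.

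A reader might infer several stronger things that the protocol does not support:

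- **That the study was planned with an 85% chance of missing a real effect.** The literal 15% power gives N of about 4, which nobody planned; the calculation used about 85%.
- **That the stated error rates are wrong in general.** Alpha = 0.05 with 1.96 is consistent for a two-sided test. Only beta and power are affected.
- **That power is stated in three ways.** Two values are stated, 15% directly and 80% through beta = 0.20. The third is implied by the Z.
- **That a null result could not be interpreted.** Such a result is read mainly from the estimate and its confidence interval, and the power used in the calculation can be recovered in any case.
- **That once the labels are corrected, 85% is this study's power.** The equation is the form for two independent means, while the Study design section fixes one group measured twice. Power for that design depends on the SD of the within-person change, and correcting the labels does not address it.

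**Conclusion.** The point holds as an error in a stated design figure. Beta = 85% with power 0.15 is a transposition, and beta = 0.20 does not belong to Z = 1.036. The values consistent with the worked line are beta = 0.15 and power = 0.85.

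The misstatement is large on paper (power of 15% or 80% against the 85% used) and nil in its effect on enrolment: 42.4 reproduces, a fully consistent calculation gives 42.6, and the planned 50 does not change. The conclusion rests only on the protocol's own equation, SD and difference and on normal quantiles. It assumes that 1.96 denotes a two-sided alpha of 0.05, which the value implies but the text does not say.

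**What to change.** In the Sample size section:

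1. In the opening sentence, state beta = 0.15 and power (1 - beta) = 0.85.
2. In the definitions under the equation, replace beta = 0.20 with beta = 0.15 and keep Z = 1.036.
3. In the worked line, either keep 1.03 with 42.4, or use 1.036 and change the result to 42.6, rounded up to 43. Changing the Z without changing the result would create a new mismatch.
4. Present the 85% as the power assumed in the equation as written, not as a demonstrated power of the one-group pre-post comparison.

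The cost is a few words of text. The planned 50, the conduct of the study and its analysis are unaffected.
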